*\*Research Electronic Data Capture (REDCap) is a research focused, electronic web-based data capture system. REDCap is a data collection tool and allows for storage and management of both surveys and databases. REDCap is a secure storage system and meets HIPAA compliance standards. REDCap software will be used to facilitate parent consents, questionnaires, and forms.*

**Materials.** The research data will include questionnaires completed by parents/caregivers both in-person and via telephone, parent hair cortisol samples, and medical chart review. Only trained project staff at each clinical site will have access to participants' identifying information.

For the hair cortisol samples, we will be following the hair collection protocol developed by [name] from the University of Massachusetts (UMASS). Hair will be cut at the level of the scalp from 2-3 locations and cut to 3cm at the distal end. Hair samples will be placed directly into a plastic vial; each vial will be labeled by an ID number uniquely linked to each study subject (see below). Hair cortisol is stable at room temperature indefinitely, thus vials will be stored in a locked file cabinet.

For the *medical chart review*, existing trained research staff members at each study site, will collect the data. We decided to use existing research staff for the data collection component of the study since getting chart review credentialing is difficult at each of the study sites. At baseline and 12-month follow-up, medical charts will be reviewed in order to determine the number of appointments kept versus cancelled or no-show, the number of days covered by prescription refills for penicillin and hydroxyurea, and blood tests for monitoring hydroxyurea (including WBC, HB F%, and MCV). At 6-month and 12-month follow-up, medical charts will be reviewed in order to determine the frequency of vaso-occlusive episodes, acute chest syndrome, and sepsis diagnoses.

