***Aim 2. Obtain population-specific empirical estimates of study parameters to plan a pragmatic large-scale cluster RCT.*** We will summarize the number of parents contacted, lost to follow-up, refusing participation, and enrolled. We will examine this by gender (e.g., father vs. mother). We will note reasons for refusals. We will determine parents' recruitment and attrition rates and receipt of WE CARE using descriptive statistics. We will also determine the data collection completion rate, including hair cortisol, for each data time point (baseline, 3-, 6-, 9-, and 12-month follow-up) via descriptive statistics. Each outcome and process variable described above will be first transformed into its final composite value/score. We will calculate within-group mean and standard deviation of our SDoH, process, mediator and health utilization and health outcome variables. We will also break down the intervention group into two subgroups differentiated by whether parents enrolled in resources at follow-up, and explore any differences. An intention-to-treat approach will be used to explore differences between the intervention and control groups. We will also report all data disaggregated by gender. Two independent sample t-test and chi-square tests will be used to determine bivariate differences. Mixed effects regression models will be used to estimate the effect size of the intervention on SCA outcomes accounting for baseline differences in sociodemographics, types of SDoH, cumulative needs, receipt of services, and *a priori* determined covariates (i.e. sociodemographic characteristics). To explore potential moderators for the intervention effect at the parent, child and family levels (e.g., gender, race, ethnicity, age, language, household income), we will use Rothman's methodology; specifically, we will conduct stratified analyses for each potential moderator followed by using standard interaction terms in our models. We will also explore mediation of our hypothesized potential mediators between SDoH and the intervention with each SCA health outcome using the approach recommended by MacKinnon, Lockwood, and Williams. We will account for the clustering by study site by calculating the intraclass correlation.

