## Statistical Power and Sample Considerations

We will enroll up to 235 subjects in this study, including up to 60 practice staff and 175 parents of children with SCA.

Because the goal for **Aim 1** is to examine the implementation of WE CARE in the outpatient pediatric hematology clinical setting our sampling will be purposeful. Based on our previous experience, we anticipate up to 15 practice staff per site will participate in focus group discussions.

For **Aim 2**, we are proposing to enroll 35 families from each of the four study sites (2 experimental, 2 control) to field test study logistics, including collecting empiric estimates of study parameters for a larger pragmatic trial. To demonstrate the feasibility of our study design, we use ED visits (primary

outcome) and penicillin adherence as examples. Assuming a 5% error rate, and based on our R00 WE CARE study, we expect a cluster coefficient no larger than 0.01. Based on recent data, we expect at least 80% of children in our control group to have at least one ED visit within our study observation period. We expect that our intervention group will have a much lower proportion, with ≤40% having with one or more ED visits. Our proposed study sample has >90% power to detect differences of at least 25% in the proportion of children with ED visits. In addition, based on estimates from the literature we expect a 9-month medication adherence of 40% and 10% in the intervention and control groups, respectively. Our study will have 90% power to detect differences of at least 20% in penicillin adherence, which is considered clinically significant. Consistent with CONSORT guidelines for pilot studies, we will not use results from this study to determine efficacy, since effects sizes from pilot studies likely overestimate or underestimate the true effect size; rather we will determine empiric estimates from the control group as the basis for power calculations for a future multi-site trial.

For **Aim 3**, in order to explore an array of beliefs and practices regarding family contextual factors that promote or prevent effective SCA management, enrollment will continue until saturation is reached (i.e. more interviews will not generate additional information) in primary research questions. Based on our previous experience, we expect 25-35 parents will be sufficient to reach saturation.

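### The stated 90% power for a 20-point difference in penicillin adherence is not reproduced: read as proportions (30% vs 10%), two-sided power is about 73-75% at the plan's cluster coefficient of 0.01 and 85-86% with no clustering

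*Combined protocol and SAP*

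**What the plan says.** The statement is in the combined protocol and SAP, Statistical Power and Sample Considerations, Aim 2. On sample size: "we are proposing to enroll 35 families from each of the four study sites (2 experimental, 2 control". On clustering: "we expect a cluster coefficient no larger than 0.01". On the expected result: "we expect a 9-month medication adherence of 40% and 10% in the intervention and control groups, respectively". The power claim follows: "Our study will have 90% power to detect differences of at least 20% in penicillin adherence, which is considered clinically significant".

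The section gives a 5% error rate without saying whether the test is one- or two-sided. It does not say whether adherence means the share of children who are adherent or a mean percentage of days, and it gives no SD. It also limits the use of the results: "we will not use results from this study to determine efficacy".

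Two places elsewhere bear on the calculation. The Data Analysis Plan for Aim 2 says: "Two independent sample t-test and chi-square tests will be used to determine bivariate differences", and on clustering: "We will account for the clustering by study site by calculating the intraclass correlation". The chart review described under Data Collection Methods, Assessments, Interventions and Schedule records "the number of days covered by prescription refills for penicillin and hydroxyurea".

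**The concern.** The section supplies nearly everything needed to check its own figure, and the natural calculation falls well short of 90%. The plan calls a 20-point difference clinically significant and presents the power figure as evidence that the design is feasible. If power at the stated clustering bound is nearer 74%, the chance of missing that difference is about 25-27% instead of 10%. A reader could then take a null adherence comparison as more informative than it is.

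**Working it through.** **Inputs** (Statistical Power and Sample Considerations unless noted)

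- n = 2 sites × 35 = 70 per arm
- control adherence p₂ = 0.10; a 20-point difference gives p₁ = 0.30
- α = 0.05, taken first as two-sided (z = 1.960), because no one-sided test is mentioned there or in the Data Analysis Plan
- cluster coefficient (ICC) from 0 to 0.01
- scale: proportion of adherent children (assumption). The plan says its 40% and 10% come from the literature, and the adherence figures cited in Background and Significance (18% for antibiotics, 41% for hydroxyurea) are proportions of children.

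**Design effect.** DEFF = 1 + (35 − 1) × ICC. At 0.01 this is 1.34, so effective n = 70/1.34 = 52.2 per arm. At 0.005 it is 1.17, giving 59.8. At 0 it is 70.

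**Formulas.** With mean proportion 0.20, the null SD is √(2 × 0.20 × 0.80) = 0.5657. The alternative SD is √(0.30 × 0.70 + 0.10 × 0.90) = 0.5477.

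- Pooled: power = Φ[(0.20√n − z × 0.5657)/0.5477]
- Unpooled: power = Φ[0.20√n/0.5477 − z]

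**Two-sided, no clustering (n = 70).** 0.20√70 = 1.673.
- Pooled: (1.673 − 1.109)/0.5477 = 1.031, power 84.9%
- Unpooled: 3.055 − 1.960 = 1.095, power 86.3%

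**Two-sided, ICC 0.01 (n = 52.2).** 0.20√52.2 = 1.446.
- Pooled: (1.446 − 1.109)/0.5477 = 0.615, power 73.1%
- Unpooled: 2.639 − 1.960 = 0.679, power 75.1%

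| 30% vs 10% (pooled / unpooled) | ICC 0 | ICC 0.005 | ICC 0.01 |
|---|---|---|---|
| Two-sided 5% | 84.9 / 86.3% | 78.8 / 80.6% | 73.1 / 75.1% |
| One-sided 5% | 91.2 / 92.1% | 87.0 / 88.1% | 82.6 / 84.0% |

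A beta-binomial simulation (400,000 runs, chi-square divided by DEFF) agrees: 86.2%, 80.3% and 74.8% two-sided. Leaving the chi-square unadjusted at ICC 0.01 gives only 82.9%, with type I error of about 9%.

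**Attempts to recover 90%**

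- *No clustering, two-sided:* required n per arm = (1.109 + 1.282 × 0.5477)²/0.20² ≈ 82, against 70 available.
- *One-sided:* 90% is reached only at an ICC of about 0.0015 (pooled) to 0.0026 (unpooled) or less.
- *20 points below the expected 40% (40% vs 20%):* two-sided power is 61-63% at ICC 0.01 and 74-75% at 0.
- *All 175 parents:* two-sided power is 92% at ICC 0 but 80% at 0.01. The Aim 2 sample is 4 × 35 = 140; adding the upper end of the 25-35 Aim 3 interviewees gives 175.
- *Mean of days covered:* the SD that gives 90% is 20 × √(n/2)/(1.960 + 1.282), which is 31.5 points at ICC 0.01 and 36.5 at 0 (31.2 and 36.2 with a t-test). At ICC 0.01, t-test power is 92% for an SD of 30 and 83% for an SD of 35.

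**What the design does deliver.** From a 10% control rate, two-sided 90% power corresponds to a difference of 25.3-26.2 points at ICC 0.01 and 21.4-22.0 points at 0. The expected 40% vs 10% has 95.4-96.5% power at 0.01.

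**Two ways these figures are favourable**

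- They count every enrolled child as a penicillin user. The inclusion criteria admit ages 0-12 on penicillin or hydroxyurea, and Background and Significance describes prophylaxis until age 5. The share on penicillin is not given. Purely as illustration, shares of 50% or 70% would put power for 20 points at about 49-52% or 61-63% at ICC 0.01.
- They use individual-level critical values. With the four sites as the units (2 degrees of freedom), power for 20 points at ICC 0.01 is about 32-34%.

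**The case against.** The strongest reply is that the scale may not be a proportion. The emergency-visit example in the same section is worded as a proportion of children, and the adherence sentence is not. Medication adherence is listed among the process measures, the Data Analysis Plan calls for group means and SDs of process variables, and the chart review captures days covered. The antibiotic figure in the Background is 18%, not 10%, so the source of the 10% cannot be seen. On a 0-100 scale with means of 10 and 30, the average SD cannot exceed √((0.09 + 0.21)/2) = 38.7 points, and it reaches that only if every child scores 0 or 100. An SD of 31 or less is therefore quite possible, and 90% power with it. This stands: the stated figure could be right on that scale. But the plan gives no SD, so the claim cannot be verified there.

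Second, the bound of 0.01 includes zero, and a one-sided test at zero clustering gives 91-92%. That may be how the figure arose. It requires a sidedness that the plan never mentions and a coefficient well below the bound quoted in the same paragraph.

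Third, the planned mixed models with baseline adjustment could raise power on a continuous scale. The power statement neither invokes nor quantifies such a gain.

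Finally, the figure is one of two examples in a pilot that disclaims efficacy testing, and the expected 30-point difference is well powered by the usual approximation. That is true and limits the weight of the point, but the sentence claims 90% for 20 points. The four-site and penicillin-share figures are side illustrations; the conclusion does not rest on them.

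**Conclusion.** The point holds. With adherence as a proportion, 70 contributing children per arm and a two-sided 5% test, power for 30% vs 10% is about 73-75% at a coefficient of 0.01 and 85-86% with no clustering. The stated 90% is not reached anywhere in the plan's own range. A one-sided test does not rescue it at 0.01 (83-84%), and a days-covered mean would need an SD that the plan does not give. Confidence in this conditional arithmetic is high; the assumptions are the proportion scale and the two-sided test. The practical consequence is modest: no decision rule depends on the figure. It still should be corrected, because it is offered as evidence of feasibility for a difference the plan itself calls clinically significant.

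**What to change.** Replace the power sentence. If adherence is a proportion and the test two-sided, it could read:

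> Treating adherence as the proportion of adherent children, with a two-sided 5% test, a cluster coefficient of 0.01 (design effect 1.34) and all 70 children per arm contributing, power is roughly 73-75% for a 20-point difference (30% vs 10%) and 90% for about 25-26 points. Power is lower if fewer children take penicillin or if inference allows for having only four sites.

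State the sidedness and the expected number of penicillin users. If a one-sided test or a mean of days covered was intended, say so, give the coefficient or SD used, and recompute on that basis.

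The cost is wording only: no added patients and no change to data collection. On the proportion reading the stated figure becomes less favourable.

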*child health are also currently unknown.* Understanding the processes linking SDoH interventions and health outcomes has the dual benefit of contributing to our scientific knowledge of SDoH and informing treatment targets in future intervention studies. Since SDoH burden falls disproportionately on those with lower socioeconomic status and on racial/ethnic minority families, it will be critical to examine these processes within diverse samples. Given the significance of this emerging field, the NIH is convening a workshop on SDoH screening and referral interventions and its future research directions in May 2018.

**Children with sickle cell anemia are the ideal population in which to study how SDoH interventions may improve health.** Sickle cell disease affects approximately 100,000 people in the US, primarily those of African and Hispanic descent. Sickle cell anemia (SCA) is the most severe form and represents approximately 60% of the sickle cell population. Manifestations of SCA, including sepsis and painful vaso-occlusive episodes, begin in infancy and expected survival is approximately 45 years, nearly 30 years less than for African Americans overall. Use of daily antibiotic prophylaxis in children with SCA until age 5 years reduces mortality, especially in early infancy. Guidelines also recommend that hydroxyurea (HU) be offered to children with SCA beginning at 9 months of age. *However, adherence to therapies proven effective for SCA is low.* One study of >2,800 eligible children with SCA found that only 18% had prescriptions filled for antibiotic prophylaxis for  $\geq 300$  days, far short of the recommended daily intake. In addition, a study of a state Medicaid program showed that only 41% of children prescribed HU were adherent, defined as supplied (from pharmacy records) to cover at least 80% of days in a year. A recent meta-analysis found mixed findings regarding the possible mechanisms underlying low rates of medication adherence among children with sickle cell disease, with medication barriers (e.g., competing demands) having the strongest effect size.

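### The stated 90% power for a 20-point difference in penicillin adherence comes out at about 73–75% on the plan's own inputs, and the scale of the adherence measure is not stated.

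*Combined protocol and SAP*

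**What the plan says.** Statistical Power and Sample Considerations uses penicillin adherence as one of two examples to show that the Aim 2 design is feasible. Its inputs are:

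- Size: "we are proposing to enroll 35 families from each of the four study sites (2 experimental, 2 control").
- Error rate: "Assuming a 5% error rate", with one- or two-sided not stated.
- Clustering: "we expect a cluster coefficient no larger than 0.01".
- Expected rates: "we expect a 9-month medication adherence of 40% and 10% in the intervention and control groups, respectively".
- Conclusion: "Our study will have 90% power to detect differences of at least 20% in penicillin adherence, which is considered clinically significant".

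No standard deviation, cut-off or unit is attached to the adherence figures. Under Data Collection Methods, the Study 2 chart review at baseline and 12 months records "the number of days covered by prescription refills for penicillin and hydroxyurea". The Aim 2 part of the Data Analysis Plan promises group means and standard deviations for process variables, a class that includes medication adherence, and adds: "Two independent sample t-test and chi-square tests will be used to determine bivariate differences". It does not say in which form adherence is compared.

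**The concern.** The 90% looks too high for a 20-point difference from a 10% control rate with an effective sample of about 52 per arm. Nor can the reader tell what quantity the figure refers to. The rates are said to come from the literature, and the adherence rates quoted in Background and Significance are shares of children above a threshold, for example "only 41% of children prescribed HU were adherent, defined as supplied (from pharmacy records) to cover at least 80% of days in a year". The neighbouring example on emergency visits is also a proportion of children. A share of adherent children is therefore the likely meaning.

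Two things are at stake. A power statement in the plan may not follow from its inputs. And the pilot exists to supply control-group estimates for sizing a larger trial; an adherence rate without a defined scale or threshold is a weak planning parameter when the underlying days are already being collected.

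**Working it through.** **Inputs.** All are from Statistical Power and Sample Considerations: 35 × 2 = 70 children per arm; cluster coefficient 0.01; control rate 10%; difference 20 points, so 10% against 30%; 5% error, taken as two-sided.

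**Effective sample.** Design effect = 1 + (35 − 1) × 0.01 = 1.34. Effective n = 70 / 1.34 = 52.2 per arm.

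**The plan's figure, as a share of children.** Power = Φ[(d − 1.96 × SE0) / SE1], with d = 0.20.

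- SE0 (pooled, mean rate 0.20) = √(2 × 0.20 × 0.80 / 52.2) = 0.0783.
- SE1 = √((0.10 × 0.90 + 0.30 × 0.70) / 52.2) = 0.0758.
- Power = Φ[(0.20 − 0.1534) / 0.0758] = Φ(0.615) = 73.1%.
- Unpooled variance gives 75.1%, the arcsine form 75.0%, and continuity correction 64.1%.

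**Can 90% be reached another way?**

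| Setting | Power, 10% v 30% |
|---|---|
| Two-sided, coefficient 0.01 | 73–75% |
| One-sided, coefficient 0.01 | 82.6% |
| Two-sided, no clustering | 85–86% |
| One-sided, no clustering | 91.2% |

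Of these, only a one-sided test that also ignores the plan's own cluster coefficient comes near 90%.

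**Detectable difference.** With the pooled formula, effective n 52.2 and control rate 10%, a 26-point difference has 89.6% power and a 26.5-point difference 90.5%. So 90% power needs about 26–27 points.

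**Children not on penicillin.** Eligibility requires daily penicillin or hydroxyurea, and the number on penicillin is not given. If 80% contribute (28 per site), effective n = 56 / 1.27 = 44.1 and power is 65.6%. If 50% contribute (17.5 per site), effective n = 35 / 1.165 = 30.0 and power is 49.1%. Both fractions are assumptions.

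**Four sites.** A site-level comparison has 4 − 2 = 2 degrees of freedom and a critical t of 4.303 instead of 1.96. With noncentrality 0.20 / 0.0758 = 2.64, power is about 32%.

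**Power on the days-covered scale.** The documents give no standard deviation or distribution, so every figure here rests on an assumption. Each case keeps 10% and 30% above the cut.

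- *Whole distribution shifts, normal:* z(0.30) − z(0.10) = −0.524 + 1.282 = 0.757 SD, giving 96.9% by t-test at n = 52.2.
- *Whole distribution shifts, beta-distributed days, cut at 80% of days or 300/365:* t-test about 95–96% and rank test about 94–98% in simulations with 52 per arm.
- *All-or-none (20% of children move from below to above the cut and no one else changes):* t-test about 39–64%, against about 75% for the share above the cut.
- *Four sites:* with 2 degrees of freedom, the normal-shift case falls to about 54%.

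**Alternative reading.** If 20% means a 20-point difference in mean days covered, power at effective n 52.2 is 99.9%, 98.3%, 92.6% and 72.4% for assumed standard deviations of 20, 25, 30 and 40 points.

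**The case against.** The strongest reply has three parts.

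First, the scale is inferred. If the 40% and 10% are mean shares of days, the stated 90% is met for standard deviations up to about 30 points. This stands: the shortfall belongs to the share-of-children reading. But the plan gives no standard deviation to support the other reading, so the 90% cannot be verified there either.

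Second, the stakes are low. The adherence figure is an illustration, the section says the pilot will not be used to judge efficacy, and at the expected 40% against 10% power is about 95% by the same method. All true. The statement about 20 points is nevertheless separate and specific, and does not follow from its inputs.

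Third, a reader might infer that the trial will dichotomise adherence, discard the days data, and forgo a gain from about 73–75% to 95–97% power. The documents do not support that. No threshold is defined for this trial, process variables are to be reported as means and standard deviations, and t-tests are listed beside chi-square tests. The 95–97% requires a shift of the whole distribution, which nothing in the documents establishes, and under an all-or-none effect the ranking reverses. Nor will penicillin days exist for every enrolled child.

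**Conclusion.** The point holds as an error in a stated power figure combined with an undefined outcome scale. Read as a share of adherent children with a 10% control rate, 70 per arm, cluster coefficient 0.01 and a two-sided 5% test, the design has about 73–75% power for a 20-point difference, not 90%; 90% requires about 26–27 points. Without clustering the figure is 85–86%. These are upper figures if some children do not take penicillin or if the analysis respects the four-site structure.

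Whether precision would be lost in the analysis is open, because the plan permits the days scale without committing to it. Any benefit of that scale depends on how the intervention changes adherence.

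**What to change.** In Statistical Power and Sample Considerations:

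- state whether the 40% and 10% are shares of children or mean shares of days, give any cut-off, and say whether the test is one- or two-sided;
- replace the 90% with the recomputed power (about 73–75% on the share-of-children reading) or the detectable difference (about 26–27 points), and state how many children are expected to be on penicillin;
- if power on the days scale is quoted, give it as a range with its assumption: about 95–97% for a whole-distribution shift, about 40–64% for an all-or-none effect.

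In the Aim 2 Data Analysis Plan, name the proportion of days covered by refills as the analysed adherence measure, separately among children prescribed each drug. Report its control-group mean, standard deviation and intraclass correlation, and keep the share above a stated cut as a descriptive planning figure.

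The cost is wording only, since the days are already abstracted. The downside is that a difference in mean days covered is less familiar to clinicians and can be less sensitive if the effect is mainly children crossing the threshold. Keeping the share alongside it lets the next trial be sized on either scale.
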